3.3.8. Time to Clinical Status Improvement

Several Secondary Endpoints involve evaluation of the time to improvement of at least one or two points on the clinical status 8-point ordinal scale. The time to improvement will be defined as the elapsed time (in days)

from randomization to the earliest day of observed improvement. Note that since clinical status assessments are recorded as defined in Section 4.3, the day that is being assessed (not necessarily the day the response is collected) will be used to determine the timing of events.

For analyses of this endpoint, imputation of the clinical score may be performed following the rules described in Section 6.5.

Any subjects that are lost to follow-up or terminated early prior to an observed improvement will be censored at the day of their last observed Clinical Status score. Subjects who complete follow-up but do not experience improvement will be censored at the day of their Study Visit Day 29. All deaths that occur on or before Study Visit Day 29 (and prior to any observed improvement) will be considered censored at Day 29.

3.3.9. Desirability of Outcome Ranking (DOOR)

The DOOR is based on categorization of the 8-point ordinal Clinical Status score, changes in the score, or combination with the occurrence (or absence) of SAEs. The DOOR category will be determined by the Clinical Status score at Baseline and at the Study Visit Day (15 and 29), and any SAEs that have occurred up to and including the respective Study Visit Day. Since this endpoint involving Clinical Status at specific timepoints, imputation of missing scores may be performed following the rules described in Section 6.5.

3.3.10. Days of Oxygen

Oxygen days will be defined as the number of days where the Clinical Status score is equal to 5, 6, or 7. The Post-Discharge Supplemental Oxygen CRF question regarding days of oxygenation (including ECMO, invasive ventilation, non-invasive ventilation, high-flow oxygen devices, and all other oxygen delivery devices) will be used for any time period the subject is not hospitalized at the study hospital. Individual subject of post-discharge oxygen use will be generated ([Listing 28](#)). The total number of days will be the sum of all reported days, regardless of whether the days occur consecutively or in disjoint intervals. See Section 6.5 for the plan for handling subjects who do not have data through Day 29 or die prior to Day 29.

3.3.11. Days of Non-Invasive Ventilation/High-Flow Oxygen

Non-invasive ventilation/high flow-oxygen days will be defined as the number of days where the Clinical Status ordinal score is equal to 6. The Post-Discharge Supplemental Oxygen CRF questions regarding days of non-invasive ventilation or high-flow oxygen will be used for any time period the subject is not hospitalized at the study hospital. The total number of days will be the sum of all reported days, regardless of whether the days occur consecutively or in disjoint intervals. See Section 6.5 for the plan for handling subjects who do not have data through Day 29 or die prior to Day 29.

3.3.12. Days of Invasive Mechanical Ventilation/ECMO

Invasive Mechanical Ventilator / ECMO days will be defined as the number of days where the Clinical Status score is equal to 7. The Post-Discharge Supplemental Oxygen CRF questions regarding days of ECMO or invasive ventilation will be used for any time period the subject is not hospitalized at the study hospital. The total number of days will be the sum of all reported days, regardless of whether the days occur consecutively or in disjoint intervals. See Section 6.5 for the plan for handling subjects who do not have data through Day 29 or die prior to Day 29.

3.3.13. Days of Hospitalization

Duration (in days) of hospitalization will be defined as the number of days subject is hospitalized for COVID-19-related reasons starting from the date of randomization. It will be calculated as the total number of days hospitalized, including readmissions for COVID-19-related reasons. It will also be calculated as the total number of days hospitalized, including any readmissions regardless of cause. See Section [6.5](#) for the plan for handling subjects who do not have data through Day 29 or die prior to Day 29.

3.3.14. Composite Endpoint of Death, SAEs, Severe AEs

A safety composite endpoint will be defined as the occurrence of at least one of the following through Day 29:

1. Death
2. SAE
3. Grade 3 or 4 treatment emergent AE

The time to this composite endpoint will be defined as the elapsed time (in days) from the day of the first dose of study treatment (baricitinib, dexamethasone, remdesivir, or placebo) to the earliest date of any of the events. Any subjects that are lost to follow-up or terminated early prior to experiencing any of the events will be censored at the day of their last observed assessment. Subjects who complete follow-up but do not experience any of the events will be censored at the Study Visit Day 29.

4. INVESTIGATIONAL PLAN

4.1. Overall Study Design and Plan

ACTT-4 will evaluate the combination of baricitinib and remdesivir compared to dexamethasone and remdesivir. Subjects will be assessed daily while hospitalized. After the subjects are discharged from the hospital, they will have a study visit at Days 15, 22, and 29 (as applicable). For discharged subjects, it is preferred that the Day 15 and 29 visits are in person to obtain safety laboratory tests and OP swab, plasma (Day 29) and serum samples for secondary research as well as clinical outcome data. However, infection control or other restrictions may limit the ability of the subject to return to the clinic. In this case, these visits may be conducted by phone, and only clinical data will be obtained. The Day 22 visit does not have laboratory tests or collection of samples and is conducted by phone.

Additionally, subjects will be contacted by phone at 2 months (Day 60) to assess long term efficacy and safety outcomes as an exploratory outcome. A chart review/extraction of data through Day 60 may be done if the subject is not available for the phone contact.

4.2. Selection of Study Population

Male and non-pregnant female adults ≥ 18 years of age or older with COVID-19 and who meet all eligibility criteria will be enrolled at up to approximately 100 clinical trial sites globally. The target population should reflect the community at large.

See Section 5.1 and 5.2 of Appendix D of the study protocol for the full list of inclusion and exclusion criteria.

4.2.1. Treatments Administered

Dosing of the medications does not need to occur at the same time. All subjects receive remdesivir as a 200 mg intravenous (IV) loading dose on Day 1, followed by a 100 mg once-daily IV maintenance dose for the duration of the hospitalization up to a 10-day total course. If subjects already received the loading dose prior to study enrollment, then start at 100 mg/day on Day 1. Any doses of remdesivir given prior to enrollment will be counted, so the total duration of remdesivir (i.e. pre-enrollment + on this trial) is 10 days (i.e., a maximum of 10 total infusions). Any doses of remdesivir were administered prior to study enrollment should be documented in Advantage eClinical as a concomitant medication given prior to Day 1. The duration of dosing may be adjusted by the site similar to what is described in the package insert and based on a subject's clinical course and ultimate disease severity.

For the baricitinib component, subjects receive either active product or placebo as follows:

- Baricitinib will be administered as a 4 mg orally (po) (two 2mg tablets) or dissolved for NG tube, daily for the duration of the hospitalization up to a 14-day total course.
- A placebo will be given as two tablets po or dissolved for NG tube, daily for the duration of the hospitalization up to a 14-day total course.
 - Any pre-study dexamethasone (max 1 dose per inclusion criteria) is not counted towards the 10-day course.

For dexamethasone component, subjects receive either active product or placebo as follows:

- Dexamethasone administered as a 6 mg slow IV push over 3 to 5 minutes daily for the duration of the hospitalization up to a 10-day total course.

- A placebo will be given as an equal volume normal saline, as a slow IV push daily for the duration of the hospitalization up to a 10-day total course.
- If site local standards use other means of administration (such as IV infusion), these may be used for both active and placebo after approval of the sponsor.
- Any pre-study dexamethasone (max 1 dose per inclusion criteria) is not counted towards the 10 day course.

Duration of therapy:

- IV remdesivir – up to 10 days while hospitalized (i.e., maximum of 10 total infusions pre-enrollment and during study).
- Oral baricitinib (or oral placebo) – 14 days while hospitalized (i.e., maximum of 14 total doses).
- IV dexamethasone (or IV placebo) – 10 days while hospitalized (i.e., maximum of 10 total doses).
- All study medications stop on discharge from hospital.
 - Of note, if a subject is retained in the hospital for non-COVID-19 related issues and no longer requires supplemental oxygen and ongoing medical care (i.e., ordinal scale category 3), the PI may decide to discontinue all medications.
- If readmitted after discharge, see Appendix D Section 7.4 of the study protocol.

4.2.2. Identity of Investigational Product(s)

See Section 6.1.1 of Appendix D of the study protocol.

4.2.3. Method of Assigning Subjects to Treatment Groups (Randomization)

Randomization will be stratified by:

- Site
- Clinical Status at enrollment (by ordinal scale)
 - Category 6: Hospitalized, on non-invasive ventilation or high flow oxygen devices, OR
 - Category 5: Hospitalized, requiring supplemental oxygen

4.2.4. Selection of Doses in the Study

The dose of remdesivir used in this study is the same dose used in previous ACTT studies, and is the US FDA approved dosage. The duration of dosing may be adjusted by the site according to clinical severity. The maximum number of doses to be given during hospitalization is ten doses. This includes the loading dose and all maintenance doses given during the study and pre-study if applicable. This study will use the same dose and duration of baricitinib that was evaluated in ACTT-2. The 4 mg daily dose of baricitinib was originally selected for use in this population of adults hospitalized with COVID-19 based on clinical data showing an inhibitory effect on cytokine signaling. This study will use the same dose and duration of dexamethasone that was evaluated in the RECOVERY trial, the largest and most influential study of dexamethasone in COVID-19.

4.2.5. Selection and Timing of Dose for Each Subject

See Sections 6.1.2 through 6.1.5 of Appendix D of the study protocol.

4.2.6. Blinding

As both arms are receiving remdesivir, the remdesivir product is not blinded and study infusions can be labeled accordingly. The baricitinib/placebo component is blinded. Baricitinib and placebo tablets are identical in appearance. The dexamethasone/placebo IV component is blinded. Dexamethasone and intravenous placebo are identical in appearance.

Unblinding of the study will occur after all subjects enrolled have reached the end of study, these visits are monitored, and data is cleaned or if the DSMB recommends unblinding. Data through Day 29 will be locked prior to the completion and lock of Day 60 data. DMID and the SDCC will be unblinded after the Day 29 database lock. Clinical sites will not be unblinded to subject-level treatment assignments until after the Day 60 database lock.

If a subject's clinical status worsens to require mechanical ventilation (ordinal 7), the treating clinician may request unblinding in order to use the prior treatment assignment to inform future treatment. See protocol Appendix D Section 6.3.2.2.

If a Serious Adverse Event occurs, that is thought to be related to the study drug, and the treating clinician believes that knowledge of the treatment arm may change the therapy provided to the patient, the individual subject can be unblinded. If unblinded for SAE, the investigator may decide to have the blinded study product and/or remdesivir infusions discontinued based on the adverse event that led to unblinding and the benefit-risk analysis. See protocol Appendix D Section 6.3.2.3.

4.2.7. Prior and Concomitant Therapy

See Section 6.5.1 of Appendix D of the study protocol for permitted concomitant therapy and procedures. See Section 6.5.2 of Appendix D of the study protocol for prohibited concomitant therapies.

4.2.8. Treatment Compliance

See Section 6.1.4 of Appendix D of the study protocol for details on dose modifications.

Each dose of study product will be administered by a member of the clinical research team who is qualified and licensed to administer the study product. Administration date and time will be entered into the case report form (CRF).

4.3. Efficacy and Safety Variables

For each study day while the patient is hospitalized, the clinical status will be recorded on an 8-point ordinal scale as follows:

- Day 1 – The clinical assessment at the time of randomization.
- Day 2+ - The most severe assessment occurring from midnight to midnight (00:00 to 23:59) of the prior day (e.g., the value recorded on Day 3 will be the most severe outcome that occurred on Day 2).

where the clinical status scale is defined as follows:

Category 8: Death;

Category 7: Hospitalized, on invasive mechanical ventilation or ECMO;

- Category 6: Hospitalized, on non-invasive ventilation or high flow oxygen devices;
- Category 5: Hospitalized, requiring supplemental oxygen;
- Category 4: Hospitalized, not requiring supplemental oxygen - requiring ongoing medical care (COVID-19 related or otherwise);
- Category 3: Hospitalized, not requiring supplemental oxygen - no longer requiring ongoing medical care. This would include those kept in hospital for quarantine/infection control, awaiting bed in rehabilitation facility or homecare, etc.;
- Category 2: Not hospitalized, but has new or increased limitation on activities and/or new or increased requirement for home oxygen over baseline, pre-COVID-19 status;
- Category 1: Not hospitalized, patient is back to their baseline, pre-COVID-19 status, that is, no new or increased limitations on activities and no new or increased oxygen use compared with baseline.

A modified version of the ordinal scale will be used in sensitivity analyses of the Key Secondary and Other Secondary Endpoints of time-to-recovery and time-to-improvement.

The “Modified Recovery” ordinal scale combines Category 1 and 3 of the original Clinical Status scale and is defined as follows:

- Category 8: Death;
- Category 7: Hospitalized, on invasive mechanical ventilation or ECMO;
- Category 6: Hospitalized, on non-invasive ventilation or high flow oxygen devices;
- Category 5: Hospitalized, requiring supplemental oxygen;
- Category 4: Hospitalized, not requiring supplemental oxygen - requiring ongoing medical care (COVID-19 related or otherwise);
- Category 3: Not hospitalized, but new or increased limitation on activities and/or requiring new or increased home oxygen;
- Category 2: Hospitalized, not requiring supplemental oxygen - no longer requires ongoing medical care; or Not hospitalized, no limitations on activities.

Desirability of outcomes response (DOOR) is an ordinal scale combining current clinical status with SAEs. SAE may be related or unrelated to study product. Any SAE occurring after study product administration through Day 15 (or through Day 29) will be counted:

- 1- Recovered (Ordinal Score Category 1,2,3)
- 2- Improved by at least 1 Ordinal Score from baseline & no SAE
- 3- Improved by at least 1 Ordinal Score Category from baseline & SAE
- 4- No change in Ordinal Score Category from baseline & no SAE
- 5- No change in Ordinal Score Category from baseline & SAE
- 6- Worsened by at least 1 Ordinal Score Category from baseline
- 7- Death (Ordinal Score Category 8)

Oxygenation, Non-invasive ventilation/high flow oxygen, Invasive Mechanical Ventilation/extracorporeal membrane oxygenation (ECMO), hospitalization and mortality will be assessed using results of the Clinical Status 8-point ordinal scale, medical history, and post discharge eCRF questions.

Safety will be assessed by the following:

- Cumulative incidence of serious adverse events (SAEs) through 28 days of follow-up.
- Cumulative incidence of Grade 3 and 4 treatment-emergent AEs.
- Discontinuation or temporary suspension of study product administration (for any reason).
- Changes in white cell count, hemoglobin, platelets, creatinine, total bilirubin, ALT, AST, and INR, d-dimer, C-reactive protein over time. Note D-dimer and CRP are not graded.
- Time to the Composite Endpoint of the first of death, SAE, or Severe AE from the day of first dose of study treatment to the earliest date of any of these events.

Clinical labs will be drawn on Days 1, 3, 5, 8, 11 and on Day 15 and 29 if the subject is able to return to the clinic or is still hospitalized. CRP values from sites using a high-sensitivity assay will be excluded from all CRP summaries and any analyses that use CRP values.

Virologic efficacy is an exploratory endpoint and will be assessed by the following:

- Qualitative and quantitative PCR for SARS-CoV-2 in OP swab on Days 1, 3, 5, 8, 11 (while hospitalized); and Day 15 and 29 (if able to return to clinic or still hospitalized).
- Qualitative and quantitative PCR for SARS-CoV-2 in blood on Days 1, 3, 5, 8, 11 (while hospitalized).

The schedule of study procedures is provided in Section 1.2 of Appendix D of the study protocol.

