3.3. Study Definitions and Derived Variables

3.3.1. Baseline Value

For efficacy assessments, the baseline value will be defined as the last value obtained prior to randomization. For safety assessments, the baseline value will be defined as the last value obtained prior to the first on-trial dose of any study product (baricitinib, dexamethasone, remdesivir, or placebo). If the exact time of the assessment or the first dose is not available, but collected on the same date, the assessment will be assumed to have occurred prior to receipt of study product.

A small subset of subjects may receive dexamethasone as standard of care on the same day as but prior to randomization then forgo the dexamethasone / placebo component of the Day 1 study product administration. For these subjects, the baseline value of efficacy assessments will be the last value prior to randomization, as in the preceding paragraph. But, for these subjects, the value of baseline safety assessments will be defined as the last value obtained prior to the dexamethasone dose. If the exact time of the assessment of the pre-randomization dexamethasone or on-trial doses of study product are not available, but collected on the same date, the assessments will be assumed to have occurred prior to receipt of study product and prior to randomization.

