3.3.2. Study Day and Time to Event

Use of "Day 29" or "Day 15" are references to actual study days and represent 28 and 14 days post-randomization, respectively. References to visits such as "Study Visit Day 29" and "Study Visit Day 15" pertain to protocol-defined visits which may occur on any day within the defined visit window and not necessarily on Day 29 and Day 15.

Time-to-event endpoints are based on actual study days, e.g., Day 29 or Day 15. Endpoints that are not specifically defined as a time-to-event are based on Study Visits, irrespective of the study day upon which the visit was conducted. As a result, time-to-event endpoints at Day 15 and Day 29 may not match corresponding Clinical Status Ordinal Scores at Study Visit Day 15 and Study Visit Day 29. For example, all subjects with Clinical Status in Category 7 or 8 recorded for Study Visit Day 29 performed on or after Day 31 may not count as events by Day 29 unless there is additional corroborating data (e.g., Death or Supplemental Oxygen Case Report Forms).

3.3.3. Mechanical Ventilation-Free Survival at Day 29

Subjects who do not report an ordinal score in Category 8 (Death) or Category 7 (hospitalized on invasive mechanical ventilation or ECMO) at any point following randomization up to and including Day 29 will be

considered to have survived free from mechanical ventilation. The proportion of subjects who survive through Day 29 free from mechanical ventilation will be estimated using a Kaplan-Meier method, allowing definition of time-to-event and time-to-censoring for all subjects.

The time-to mechanical ventilation or death is defined as the elapsed time in days from randomization to the earliest day at which the subject requires mechanical ventilation or dies. The day the subject requires mechanical ventilation is defined as the first day reporting an ordinal score in Category 7. Note (as in Section 3.3.4), this should be the date the subject is assessed, and not the date the score is reported. The time-to-event for subjects discharged to hospice or other end-of-life care prior to Day 29, but for whom a death date is unknown and with Day 60 data unavailable, will be the number of days from randomization to discharge.

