3.3.4. Clinical Status Ordinal Score at Specific Timepoints

The Primary Endpoint, Key Secondary Endpoint, and several other Secondary Endpoints rely on evaluation of the Clinical Status ordinal score at specific days. For these endpoints, the Study Visit Day is the timepoint of interest, not the actual study day (e.g., Study Visit Day 29 as opposed to study day 29). The Clinical Status Score collected at the Study Visit corresponding to the specific endpoint will be used for the outcome. Specifically, results from Study Visit Day 29 will be used for the Primary Endpoint and results from Study Visit Day 15 will be used for the Key Secondary Endpoint, with these and other Study Visit Days (3, 5, 8, 11, 22) used for other Secondary Endpoints. For analyses involving Clinical Status at specific timepoints, imputation of missing scores may be performed following the rules described in Section 6.5.

3.3.5. Progression to Clinical Status Category 6, 7, or 8 by Day 29

This Secondary Endpoint will be assessed similarly to Mechanical Ventilation-free survival (Section 3.3.2), but the event of interest is any report of a Clinical Status ordinal score in Category 8 (Death), Category 7 (invasive mechanical ventilation or ECMO), or Category 6 (non-invasive ventilation or high-flow oxygen device). This endpoint will only be assessed in those with actual baseline Clinical Status in Category 5 (hospitalized, requiring supplement oxygen).

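### The score recorded on Day 2 covers all of calendar Day 1, so high-flow or non-invasive support that ended before randomization is counted as progression in the third-ranked test

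*SAP*

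**What the plan says.** - **Baseline.** For efficacy, Section 3.3.1 states that "the baseline value will be defined as the last value obtained prior to randomization". Section 4.3 defines the first score as "Day 1 – The clinical assessment at the time of randomization".
- **Later records.** Section 4.3 defines them as "Day 2+ - The most severe assessment occurring from midnight to midnight (00:00 to 23:59) of the prior day" and illustrates this: "the value recorded on Day 3 will be the most severe outcome that occurred on Day 2". No exception is made for the record that covers Day 1.
- **Day numbering.** Section 3.3.2 says that Day 29 and Day 15 "represent 28 and 14 days post-randomization, respectively", so Day 1 is the calendar day of randomization.
- **Third-ranked endpoint.** Section 3.3.5, restricted to actual baseline category 5, says that "the event of interest is any report of a Clinical Status ordinal score in Category 8 (Death"), and extends this to Categories 7 and 6. It is to be assessed in the same way as ventilation-free survival.
- **Primary endpoint.** Section 3.3.3 limits events to the period after randomization, dates a score by the day assessed, and adds: "The day the subject requires mechanical ventilation is defined as the first day reporting an ordinal score in Category 7".
- **New use.** Sections 8.2.12 and 8.2.14 identify new high-flow/NIV use and new invasive ventilation by a score of 6 or 7 after randomization.
- **Hierarchy.** Section 6.8 places non-progression to 6, 7 or 8 third of five, ahead of mortality and time to recovery.

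**The concern.** The baseline score is taken at a point in time. The next score is a 24-hour maximum over a window that starts before that point. A subject who was stepped down from high-flow to low-flow oxygen in the hours before randomization can therefore be baseline 5 with a first follow-up record of 6, although support only fell.

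The assigned treatment cannot influence such an event. Mixing these events into a between-arm comparison adds the same noise to both arms and pulls the contrast toward no difference. The endpoint affected sits in the confirmatory sequence. If the first two tests succeed and this one is missed, mortality and recovery cannot be formally tested.

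**Working it through.** **Tracing the rules for one subject.** High-flow oxygen in the morning of Day 1, low-flow by noon, randomized at 15:00, never escalated again.

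1. Baseline (3.3.1, 4.3): status at 15:00, category 5. The subject enters the Section 3.3.5 analysis.
2. Day 2 record (4.3): worst status from 00:00 to 23:59 of Day 1, category 6.
3. Event (3.3.5): a report of category 6 exists, so the subject has progressed. Under the date-assessed rule in 3.3.3 the event falls on Day 1 (time 0). Under the convention in the worked example of 3.3.7, where a score recorded on Day 4 gives 3 days, it falls at 1 day. Both count it.
4. New use (8.2.12): the record was made after randomization with a score of 6, so the subject is a new high-flow/NIV user.
5. Exits: the missing-data rules in 6.5 do not address the case. The committee triggers named in 3.3.3 are gaps in scores while hospitalized, early termination while hospitalized, and an incomplete Day 29 or hospice discharge with unknown death date. Beyond these there is only discretionary review of other special cases.

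**Reach into other endpoints.**
- Days of oxygen (3.3.10) count 5, 6 and 7 alike, so a 6 in place of a 5 changes nothing.
- Days of NIV/high-flow (3.3.11) can gain at most one day.
- The primary endpoint needs invasive ventilation or ECMO earlier on the randomization day in a subject scored 5 or 6 at randomization, which should be very rare.

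**Size, as an illustration only.** The plan states no figure to reproduce here. It gives neither the share affected (f), nor the 6/7/8 event rates, nor the size of the baseline-5 stratum. Assumptions: true progression 25% (dexamethasone) vs 18% (baricitinib); 550 per arm, about 80% of the 691 per arm implied by the planned 1382; no censoring; the same f in both arms; earlier support unrelated to later progression.

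Observed event-free proportion: S′ = S(1 − f).
Contrast: c = log(−log S′dex) − log(−log S′bari).
Variance per arm (Greenwood, transformed): (1 − S′)/(n S′ (log S′)²).
Power ≈ Φ(c/SE − 1.96).

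| f | S′ dex | S′ bari | difference (points) | c | SE | c/SE | power |
|---|---|---|---|---|---|---|---|
| 0 | 0.7500 | 0.8200 | 7.00 | 0.371 | 0.132 | 2.81 | 80% |
| 1% | 0.7425 | 0.8118 | 6.93 | 0.356 | 0.130 | 2.75 | 78% |
| 3% | 0.7275 | 0.7954 | 6.79 | 0.329 | 0.125 | 2.63 | 75% |
| 5% | 0.7125 | 0.7790 | 6.65 | 0.306 | 0.121 | 2.52 | 71% |

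The contrast shrinks by 4%, 11% and 18% at f = 1%, 3% and 5%. Wholly false events, meaning subjects who would not otherwise have progressed, make up f × 0.75/(1 − S′dex) of dexamethasone-arm events: 0.0075/0.2575 = 3%, 0.0225/0.2725 = 8%, 0.0375/0.2875 = 13%.

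**Range over other assumed rates** (same scale, 553 per arm, f = 0, 1%, 5%): 15% vs 10% gives power of 70.3%, 67.1%, 55.6%; 30% vs 24% gives 61.1%, 59.5%, 53.7%. The loss is about 2 to 3 points at f = 1% and 7 to 15 points at f = 5%.

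**The case against.** The strongest reply is that the SAP already excludes these events. Section 3.3.3 speaks only of events after randomization, 3.3.5 follows it, and 8.2.12 and 8.2.14 ask for a post-randomization score. This establishes the intent, and that part stands. It does not give a derivation. The daily score is one worst value without a clock time, and the Day 2 record is itself made after randomization, so a programmer following 4.3 and 3.3.5 would count it.

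Second, the blinded Endpoint Review Committee may look at other special cases. That route is real, but nothing requires these cases to be sent there.

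Third, the protocol or case report form may restrict the Day 1 window or capture start times. That cannot be excluded, since neither is shown. The SAP nevertheless states the window in full, with an example, and that statement does not fit its own event definition.

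Fourth, the frequency is unknown and may be very low. This stands, and it limits how much weight the power figures can bear.

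A reader might infer more than the document supports:
- **Bias or false positives.** Support before randomization cannot depend on the assigned arm, so neither bias toward one arm nor type I error inflation follows.
- **A compromised primary endpoint, or distorted oxygen days.** The first would be very rare and the second does not occur when a 6 replaces a 5.
- **A known loss of power.** Nothing in the SAP supports any particular value of f.

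**Conclusion.** The definitions do not fit together. Section 4.3 lets the first follow-up score look back before randomization, while 3.3.3 and 3.3.5 intend only what comes after. Followed as written, the plan counts some step-downs before randomization as progression to category 6 and as new high-flow/NIV use.

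The consequence is non-differential dilution of the third test. It matters for the later tests only if the primary and the Day 15 ordinal tests have both rejected. The loss from 80% to between 78% and 71% power rests on assumed event rates, stratum size and an affected share of 1% to 5%. If subjects stepped down on Day 1 are also more likely to progress later, fewer of these events are wholly false and the loss is smaller. The inconsistency is worth correcting because the correction is cheap, not because a large effect has been shown.

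**What to change.** 1. In Sections 4.3, 3.3.3, 3.3.5, 8.2.12 and 8.2.14, state that the score covering Day 1 counts only status from randomization to 23:59 of that day.
2. The SAP does not show that start times of in-hospital oxygen support are recorded, and Section 15.3 says enrolment was complete at the Version 2.0 update, so some Day 2 records may not be separable. For these, make a Day 2 record worse than baseline a named trigger for blinded Endpoint Review Committee review.
3. Add a sensitivity analysis of the Section 3.3.5 endpoint that excludes Day 1 events the committee cannot resolve.
4. Do not solve the problem by requiring the Day 3 record to be worse than baseline as well. That makes an event depend on later status and discards true escalations after randomization that resolve the same day.

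The change should be settled before the Day 29 lock, after which Section 4.2.6 has the sponsor and the coordinating center unblinded. It costs one sentence in each affected section, one sensitivity analysis and a few more cases for the committee. It changes nothing in patient management.
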